14.4.3. Subject Demographic and Disposition Data

Demographic data and baseline characteristics including age, sex, race or ethnicity, height, weight, and BMI will be summarized by treatment cohort and overall.

Subject disposition will be presented by treatment cohort and overall. The number of subjects who completed the study and those that discontinued from the study will be provided. The reasons for early discontinuation also will be presented. A tabulation of the number of subjects exposed to study drug and duration of exposure will also be presented for each treatment cohort and overall. Treatment adherence, dose interruptions, and reasons for dose interruptions will be provided as summaries or listed as appropriate.

14.4.4. Analysis of Efficacy Variables

The efficacy analyses will be based on the FAS population. Efficacy data will be summarized by treatment cohort and study visit.

For continuous variables, descriptive summaries (for the recorded value, change from baseline, and percentage change from baseline) will be presented by study visit and treatment cohort. For specific parameters of interest, point estimates for the changes and percent changes from baseline will be summarized along with their 80% CIs, 95% CIs and p-values using the one-sample t-test.

For binary endpoints (eg, uPCR response), summaries will be presented as counts and frequencies by post-baseline visit and treatment cohort. Corresponding confidence intervals (80% and 95%) will be provided for specific parameters of interest using the Clopper-Pearson Exact method.

Categorical data will be summarized by study visit and treatment cohort using counts and percentages or descriptively (depending on the number of categories and whether the categories are nominal or ordered). Details will be provided in the SAP.

Plots of individual efficacy assessments over time with an overlay of the group mean will be provided by treatment cohort. Results will be presented by parameter, with all time points reported.

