6.2.1. Primary Endpoints

The primary endpoint of this study is:

• Change in 24-hour urinary protein excretion normalized to urine creatinine as measured by percentage change in uPCR from baseline

[figure not shown]

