3.3. Statistical Hypotheses

Protocol states post-baseline measurements were to be assessed against their applicable baseline measurements.

Due to the study discontinuation at a total of 2 treated subjects, formal statistical hypotheses will not be conducted.

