6.7.3. Change from Baseline, Percent Change from Baseline and Ratio to Baseline

The following changes from baseline will be derived:

- Change from baseline will be calculated as (post-baseline result baseline result)
- Percent change from baseline will be calculated as (change from baseline/baseline result * 100)
- Ratio to baseline will be calculated as post-baseline result divided by baseline result

If either the baseline or the post-baseline result is missing, then the changes from baseline described above will be missing. If the baseline value is 0, the percent change from baseline or ratio to baseline will be missing.

Note: The CKD-EPI formula will use the serum creatinine in the computation of eGFR included in the efficacy summary table.

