7. GENERAL CONSIDERATIONS FOR DATA ANALYSES

Continuous variables (eg, age) are summarized using descriptive statistics (the number of subjects with available data, the mean, standard deviation (SD), median and minimum and maximum). Categorical variables (eg, race) are summarized using counts and percentages.

The following conventions are applied to all data presentations and summaries.

- For continuous variables, all mean and median values are formatted to one more decimal place than the measured value. Standard deviation values are formatted to two more decimal places than the measured value. Minimum and maximum values are presented with the same number of decimal places as the measured value.
- For categorical variables, the number and percentage of responses are presented in the form XX (XX.X%) where the percentage is in the parentheses.
- Date variables are formatted as DDMMMYYYY for presentation. Time is formatted to 24-hour format as HH:MM for presentation, if applicable.
- Wherever possible, data will be decimal aligned.
- Any row with all zeros will not appear except with reasons for not completing the study. Summary tables will clearly indicate the number of subjects to which the data apply. If a table, listing, or figure has no available data, then the body should read 'No data to report.'

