7.1. Treatment group Descriptors

There were only 3 screened subjects who had historical C3G in this study. Two of them had confirmed C3G per central pathologist and started BCX9930 under 500 mg BID. The unconfirmed C3G subject was a screen failure. No subjects were enrolled under the other two cohorts (IgAN and PMN).

Disposition summaries will be presented by the 'C3G' cohort and all screened subjects.

Demographics and baseline characteristics summaries will be presented by the 'C3G' cohort. All other summaries will be presented by the following dosing groups:

- C3G 500 mg BID
- C3G 500 mg Total Daily Dose
- Total All Doses (Efficacy summaries will not have this column).

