9. EFFICACY

Due to the study discontinuation at a total of 2 treated subjects, efficacy analysis will be limited to descriptive statistics for the following key efficacy endpoints: 24-hour uPCR, 24-hour urine protein excretion and eGFR.

Descriptive statistics will be presented on observed values, change from baseline, percent change form baseline and ratio to baseline by scheduled visit using nominal visits. Source data of these key efficacy endpoints will be listed.

Source data collected for all other efficacy endpoints will be listed.

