10.3. Concomitant and Other Medications

Any medication that was ongoing, started, or ended on or after the initiation of study drug will be considered concomitant. Concomitant medications will be summarized by dosing groups.

For the subject who received study drug under two different dosing groups, medications taken on or after the initiation of study drug in the first dosing group through one day before the start of the second dosing group will be considered concomitant medications for the first dosing group. Medications taken on or after the start of the second dosing group will be considered concomitant medications for the second dosing group.

Concomitant medications will be listed.

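### Should percent change in proteinuria be analysed on the log scale, and the ratio to baseline summarised by a geometric mean?

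*Protocol*

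**What the plan says.** The primary endpoint (Protocol section 6.2.1) is "Change in 24-hour urinary protein excretion normalized to urine creatinine as measured by percentage change in uPCR from baseline". Protocol section 14.4.4 plans descriptive summaries by visit and cohort. For parameters of interest that it does not name, it adds that changes and "percent changes from baseline will be summarized along with their 80% CIs, 95% CIs and p-values using the one-sample t-test". No transformation is mentioned. Section 14.2 gives no power calculation; about 14 subjects per cohort are meant to provide an estimate of uPCR reduction. Section 14.4 leaves the detailed methods to the SAP.

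The SAP was written after development stopped. Section 3.3 states: "Due to the study discontinuation at a total of 2 treated subjects, formal statistical hypotheses will not be conducted". Section 9 limits efficacy to descriptive statistics for 24-hour uPCR, 24-hour urine protein and eGFR, given as observed values, "change from baseline, percent change form baseline and ratio to baseline by scheduled visit". Section 6.7.3 defines the last of these: "Ratio to baseline will be calculated as post-baseline result divided by baseline result". Section 7 sets the summary statistics for continuous variables as the number of subjects with data, "the mean, standard deviation (SD), median and minimum and maximum".

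On dosing groups, section 7.1 says of the screened subjects: "Two of them had confirmed C3G per central pathologist and started BCX9930 under 500 mg BID". Section 10.3 has a rule that begins "For the subject who received study drug under two different dosing groups", so one of the two treated subjects appears to contribute to both the 500 mg BID and the 500 mg total daily dose columns.

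**The concern.** Two things catch the eye.

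First, a ratio measure such as uPCR is often skewed, and percent change inherits the skew. The mean percent change then depends on the spread between subjects as well as on the typical change, and a t-interval on that scale can miss its nominal coverage in a small cohort. In a proof-of-concept study meant to inform the size of later trials, a diluted estimate of reduction and a lopsided interval would matter.

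Second, the SAP adds a ratio to baseline next to percent change but summarises it with arithmetic statistics only. The usual reason to show a ratio is to average it on the log scale. Without that, the ratio rows repeat the percent-change rows in other units.

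**Working it through.** **No figure to reproduce.** The documents state no power, standard deviation or expected effect. Everything below on coverage and power therefore rests on assumed distributions.

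**1. The redundancy is exact.** From SAP section 6.7.3, percent change = 100 × (post − baseline)/baseline = 100 × (ratio − 1), and both quantities are missing under the same conditions. So the mean, median, minimum and maximum of the ratio each equal 1 + (the same statistic of percent change)/100, and SD of the ratio = (SD of percent change)/100. No assumption is needed.

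**2. What the protocol's t-interval would have done at n = 14.** Assume log-normal ratios with geometric mean 0.70 (a 30% reduction). The arithmetic mean percent change is 100 × (0.70 × exp(s²/2) − 1), where s is the log-SD.

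| log-SD | Arithmetic mean change | 95% t-interval coverage, percent change | Same, log ratio | Power, percent change v log ratio |
|---|---|---|---|---|
| 0.4 | -24.2% | about 93% | 95% | 73% v 87% |
| 0.6 | -16.2% | about 91% | 95% | 31% v 54% |
| 0.8 | -3.6% | about 89% | 95% | 14% v 34% |

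Each coverage figure is for that interval's own target (arithmetic or geometric mean). The two tests have different null hypotheses: mean change 0, and geometric ratio 1.

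**3. The same check under another assumption.** Let the ratios be symmetric on the raw scale: normal, centre 0.70, truncated to 0.05–1.35, n = 14, with SD 0.2, 0.25, 0.3 and 0.4 in turn. The 95% coverage is then about 95% throughout for percent change, and about 94%, 93%, 93% and 92% for the log ratio. At SD 0.3 power is about 97% for both. The ranking in step 2 therefore comes from the log-normal assumption, and the documents support neither assumption over the other.

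**4. What will be reported.** Two subjects were treated. At n = 2 a 95% t-interval would have half-width 12.706/√2 = 8.98 SD, so leaving intervals out is sensible.

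For two ratios a and b, the arithmetic change is (a + b)/2 − 1 and the geometric change is √(ab) − 1. The ratios below are illustrative.

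| Ratios | Arithmetic | Geometric |
|---|---|---|
| 0.5 and 2.0 | +25% | √1.00 − 1 = 0% |
| 0.5 and 1.5 | 0% | √0.75 − 1 = -13.4% |
| 0.6 and 0.8 | -30.0% | √0.48 − 1 = -30.7% |

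With n = 2 the median equals the mean and gives no separate view. But the minimum and maximum are a and b themselves, so the geometric mean is √(minimum × maximum), read straight from the table. In a column with one subject all these means coincide. On the reading of section 10.3 above, that is the total daily dose column, so the two means can differ only at visits where both subjects have 500 mg BID data.

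**The case for a change.** The strongest case for acting is that the remedy is almost free: one log transform, no new data, and a back-transformed geometric mean is still a percent change, so the endpoint is kept. The direction of the difference needs no distributional assumption, because the arithmetic mean ratio exceeds the geometric mean whenever subjects differ. With two subjects who move in opposite directions, the printed mean could suggest a rise where the geometric change is nil. The protocol text might also be reused in a later study.

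Much of this stands as general advice. A log-scale analysis would be a reasonable choice for a full trial in proteinuria, and a geometric mean would be the more useful summary in the ratio rows. It does not show a fault that needs correcting here. The arithmetic mean of percent change is a legitimate target for an endpoint defined as percent change; its dependence on spread is a property of that target. Protocol section 14.4.4 names neither the parameters nor a transformation and defers to the SAP, and the SAP set the t-analysis aside for a stated reason. A geometric mean would also leave the median, SD, minimum and maximum of the ratio as redundant as before. Finally, the table specifications listed under SAP section 14.2 are not in the text available for review, so the table may already include one.

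**Conclusion.** No change is called for. The t-analysis in Protocol section 14.4.4 will not be run, so rewording it would alter no reported number. Its weakness at n = 14 (95% coverage of about 89% to 93%) holds under log-normal ratios with log-SD 0.4 to 0.8; under ratios symmetric on the raw scale the log-ratio interval is the one that falls short, at about 92% to 94%.

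The redundancy in SAP sections 6.7.3, 7 and 9 is real and exact, but it is harmless. Following the SAP as written gives correct numbers, both individual values can be read from the minimum and maximum, and the source data are listed. A geometric mean for 24-hour uPCR and 24-hour protein would be an optional courtesy to the reader. It would change no conclusion from a two-subject descriptive report that focuses on safety. This rests on the SAP's statement that two subjects were treated, and on reading section 10.3 to mean that only one of them also received the second dosing regimen.

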14.4.5. Analysis of Safety Variables

The safety analyses will be analyzed by treatment cohort and overall.

Safety endpoints that will be summarized include, at a minimum, the number and proportion of subjects: 1) with a TEAE; 2) who discontinue BCX9930 due to a TEAE; 3) who experience a TESAE; 4) who experience a treatment-emergent Grade 3 or 4 AE; and 5) who experience a treatment-emergent Grade 3 or 4 laboratory abnormality. In addition, the proportion of subjects with a treatment-emergent, treatment-related AE consistent with a drug rash will also be summarized.

Adverse events will be mapped to a Medical Dictionary for Regulatory Activities (MedDRA) preferred term and system organ class (SOC). The occurrence of treatment-emergent AEs will be summarized using MedDRA preferred terms, SOCs, and severity. Separate summaries of TEAEs, TESAEs, AEs considered to be related to study drug, and AEs leading to study drug interruption will be generated. All AEs will be listed for individual subjects showing both verbatim and preferred terms.

Descriptive summaries (actual and change from baseline) of vital signs, weight, bedside ECG parameters, and clinical laboratory results will be presented. Laboratory and ECG abnormalities will be graded according to CTCAE (Version 5.0, 27 November 2017).

Any graded abnormality that occurs following the initiation of study drug and represents at least a 1-grade increase from the baseline assessment is defined as treatment emergent. The number and percentage of subjects experiencing treatment-emergent graded toxicities will be summarized. Laboratory toxicity shifts from baseline to worst post-baseline assessment will be summarized.

Clinically significant abnormal morphological ECG findings will be summarized.

The change from baseline in QTcF will be determined by ECGs. At each time point ECGs are analyzed, an individual subject's change from baseline will be calculated as:

 Δ_{ik} = (QTcF for subject at time point k – baseline QTcF)

Where QTcF measurements will be the average of triplicate ECGs at baseline, and single values at each time point.

For routine ECGs, the number and proportion of subjects with QTcF \leq 450, > 450 to \leq 480, > 480 to \leq 500, and > 500 msec; or changes of \leq 30, > 30 to \leq 60, or > 60 msec will be summarized.

Physical examination findings will be listed.

Concomitant medications will be coded using the World Health Organization drug dictionary and summarized.

As applicable, safety data will be summarized by treatment cohort and overall.

No formal tests of hypothesis are planned for safety data.

14.4.6. Patient-reported Outcomes

Patient-reported outcomes (will be summarized descriptively (actual and change from baseline, as applicable) by study visit and treatment cohort.

14.4.7. Pharmacokinetic Analyses

Sparse plasma and spot urine samples will be collected for analysis of BCX9930 and metabolite concentrations as described in Table 2 and Table 3.

Sparse plasma and urine PK data will be listed.

Subjects enrolled in the PK/PD substudy will have plasma and urine samples collected as described in Table 4. Plasma concentration data will be summarized by visit (first dose vs. steady state) and nominal timepoint. Urine concentration data will be summarized by visit and void (first or second void within the sample collection period).

Plasma PK data collected from this study may be pooled with other clinical studies to develop population PK models. These analyses will be reported separately from the CSR.

Further details of the PK data analyses for this study will be included in a specific analysis plan.

14.4.8. Pharmacodynamic and Biomarker Analyses

Descriptive summaries (actual, change from baseline, and percentage change from baseline) will be presented by parameter, time point, and treatment cohort (and overall) for each PD parameter. Point estimates and 95% CIs will be presented for change from baseline and percentage change from baseline by parameter, post-baseline study visit, and treatment cohort.

Plots of individual and mean PD assessments and biomarkers over time will be provided by treatment cohort.

PD data may be analyzed in combination with data from other studies as appropriate (which may include model-based analyses of population PK and/or PK/PD). These analyses will be reported separately from the CSR.

15. STUDY ADMINISTRATION

15.1. Study Monitoring

Before an investigational site can enter a patient into the study, a representative of BioCryst will assess the investigational study site to:

- Determine the adequacy of the facilities
- Discuss with the investigator(s) and other personnel their responsibilities with regard to protocol adherence, and the responsibilities of BioCryst or its representatives. This will be documented in a Clinical Study Agreement between BioCryst and the investigator.

During study conduct, BioCryst or its designee will conduct periodic monitoring visits to ensure that the protocol and Good Clinical Practice (GCP) are being followed. The monitors will review source documents to confirm that the data recorded on eCRFs are accurate. The investigator and institution will allow BioCryst representatives, monitors, or its designees direct access to source documents to perform this verification.

It is important that the investigator(s) and their relevant personnel are available during the monitoring visits and that sufficient time is devoted to the process.

During the study, a monitor from BioCryst or representative will have regular contacts with the investigational site personnel, for the following:

- Provide information and support to the investigator(s)
- Confirm that facilities remain acceptable
- Confirm that the investigational team is adhering to the protocol, that data are being accurately recorded in the eCRFs, and that investigational product accountability checks are being performed
- Perform source data verification. This includes a comparison of the data in the eCRFs with the subject's medical records at the hospital or practice, and other records relevant to the study. This will require direct access to all original records for each subject (eg, clinic charts).
- Record and report any protocol deviations not previously sent to BioCryst.
- Confirm AEs and SAEs have been properly documented on the eCRFs and confirm any SAEs have been forwarded to BioCryst and those SAEs that met criteria for reporting have been forwarded to the IEC/IRB.

The representative(s) of BioCryst or its designee will be available between visits if the investigator(s) or other staff needs information or advice.

15.2. Audits and Inspections

Authorized representatives of BioCryst, US FDA and other regulatory authorities, and/or ethics committees may visit the site to perform audits or inspections, including source data verification. The purpose of a BioCryst audit or inspection is to systematically and independently examine all study-related activities and documents to determine whether these activities were conducted, and data were recorded, analyzed, and accurately reported according to the protocol, standard operating procedures, ICH/GCP guidelines, and any applicable regulatory requirements. The investigator will permit study-related audits mandated by the sponsor, after reasonable notice, and inspection by domestic or foreign regulatory authorities. The investigator should contact BioCryst immediately if contacted by a regulatory agency about an inspection.

It is important that the investigator and relevant personnel are available during the possible audits or inspections and that sufficient time is devoted to the process.

15.3. Ethics Committee

Ethics approval for the investigation must be obtained prior to commencing the study. Initial ethics approval, and all materials approved by the ethics committee, including the ICF and any recruitment materials, must be maintained by the investigator and made available for inspection.

15.4. Serious Breaches of GCP

It is the responsibility of the sponsor to notify the competent authority of any serious breach of GCP that is likely to affect, to a significant degree, the safety or mental integrity of the subjects of the study or the scientific value of the study. All serious breaches will be notified to the relevant competent authority in accordance with locally applicable regulations. The reporting to the sponsor will be performed by the party who suspects the serious breach.

16. QUALITY CONTROL AND QUALITY ASSURANCE

During study conduct, BioCryst or its designee will conduct periodic monitoring visits to ensure that the protocol and GCP are being followed as described in Section 15.1.

To ensure compliance with GCP and all applicable regulatory requirements, BioCryst or its designee may conduct a quality assurance audit. Please see Section 15.2 for more details regarding the audit process. The investigator agrees to allow the auditors to inspect the drug storage area, study drug stocks, drug accountability records, subject charts and study source documents, and other records relative to study conduct.

17. ETHICS

17.1. Ethics Review

The final study protocol, including the final version of the ICF, must be approved or given a favorable opinion in writing by an ethic committee, as appropriate. For the purposes of this protocol, "ethics committee" describes the applicable governing IRB, REB, or IEC. The

investigator must submit written approval from the ethics committee to BioCryst before he or she can enroll any subject into the study.

The ethics committee will be informed of any amendment to the protocol in accordance with local requirements. In addition, the ethics committee must approve all advertising used to recruit subjects for the study. The protocol must be re-approved by the ethics committee upon receipt of amendments and annually, as local regulations require.

The ethics committee will be provided with reports of any reportable serious adverse drug reactions from any other study conducted with the investigational product, in accordance with local regulations. BioCryst will provide this information to the investigator.

Progress reports and notifications of serious adverse drug reactions will be provided to the ethics committee according to local regulations and guidelines.

